11.1.4 Protocol Version 4.0

Procedures	Screen/ BL	Cycle #1		OP ¹ #1	Cycle #2		OP #2			LTFU		
		Dosing every 2-3 days			Home images	Dosing every 2-3 days		At-home monitoring and monthly on-site visits				
		≤ 3 months			Variable	≤ 3 months		3 months after C2 ²				
Procedures	Screen/ BL	Dose days	Last dose	OP 1	Dose days	Last dose	C2 +1mo	C2 +2mo	C2 +3mo	LTFU		
Urine Pregnancy Test	X											
HIV, Hep B, Hep C Testing	X											
Hematology & Chemistry ³	X		X			X	X	X	X			
COL7 Antibody Assay	X		X			X	X	X	X			
HSV Antibody Assay	X		X			X	X	X	X			
Wound Area Assignment	X											
Pre-dose Tattoos	X											
Concomitant Medications	X	X	X		X	X	X	X	X			
Adverse Events	X	X	X		X	X	X	X	X			
Viral shedding (skin swab)	X	X	X		X	X	X	X	X			
Viral shedding (blood and urine)	X		X			X	X	X	X			
Physical Exam	X								X			
PRO Assessment	X	X	X		X	X	X	X	X			
Global Wound Assessment	X	X	X		X	X	X	X	X			
Vital Signs	X	X	X		X	X	X	X	X			
At-home wound imaging ⁴		X	X	X	X	X	X	X	X			
On-site wound imaging	X	X	X		X	X	X	X	X			
Wound stenciling	X	X	X		X	X	X	X	X			
IP Administration	X	X	X		X	X	X	X	X			
Wound biopsy ⁵	X		X			X	X	X	X			

¹ OP = Observation Period

² Visit windows for the OP2 visits are +/- 1 week

³ After screening/baseline, performed only as clinically indicated to minimize blood draws

⁴ At-home wound imaging occurs throughout the study during bandage changes

⁵ Biopsies are performed at the discretion of the Investigator and Sponsor.

11.2 Appendix 2: Adverse Event and Prior/Concomitant Medication Date Imputations

Adverse Event Start/Stop Date Imputation

Imputation Rules for Partial Dates (D = day, M = month, Y = year)

Parameter	Missing	Additional Conditions	Imputation
Start date for AEs	D	M and Y same as M and Y of first dose of study drug	Date of first dose of study drug
		M and/or Y not same as date of first dose of study drug	First day of month
	D and M	Y same as Y of first dose of study drug	Date of first dose of study drug
		Y prior to Y of first dose of study drug but same as Y of screening date	Date of screening date
	D, M, Y	None - date completely missing	Date of first dose of study drug
Stop date for AEs	D	M and Y same as M and Y of last dose of study drug	Date of last dose of study drug
		M and/or Y not same as date of last dose of study drug	Use last day of month
	D and M	Y same as Y of last dose of study drug	Date of last dose of study drug
		Y not same as Y of last dose of study drug	Use Dec 31
	D, M, Y	None - date completely missing	No imputation, but assume ongoing

Note: In all cases, if an estimated start date is after a complete stop date, use the first day of the stop date month.

Similarly, if the estimated stop date is before a complete or imputed start date, use the last day of the start date month.

In all cases, if it cannot be determined if the adverse event occurred prior to or after the first dose of test article, the adverse event should be defined as treatment emergent.

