### 10.6.1 Adverse Events

Adverse events are coded using the MedDRA adverse event dictionary. Safety evaluations are based on occurred adverse events, laboratory values, vital signs and appearance of collagen VII antibodies, and RCV. Severities of toxicities is described using the NCI Common Toxicity Criteria (CTC) grades.

Adverse events are grouped into pre-treatment adverse events and treatment-emergent adverse events and are tabulated by preferred terminology and by body system for each study phase. The number of adverse event entries, as well as the number of patients are reported. Analyses include tabulation of adverse event type, relationship to KB103, seriousness, and severity of adverse events according to CTCAE.

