9.1 Adverse Events

Verbatim descriptions of AEs will be coded using MedDRA, version to be delineated in the CSR. Summary tables will be provided for all treatment-emergent adverse events (TEAEs), but all AEs will be provided in a listing. A treatment-emergent AE is defined as any AE that newly appeared, increased in frequency, or worsened in severity on or after the initiation of active test article. An AE is considered treatment emergent if the AE start date and time is on or after the start date and time of the first administration treatment dose. If time of the AE is missing and it occurred on the same date as the first administration treatment dose, the AE will be defined as treatment emergent. If the start date of the AE is partial or missing and it cannot be determined if the AE occurred prior to or after the first administration treatment dose, the AE should be defined as treatment emergent.

An overall summary of AEs will include the number of subjects who experienced at least one AE of the following categories: any AE, any TEAE, any drug-related TEAE, any severe TEAE, any serious TEAE, any drug-related SAE, any serious TEAE leading to death, any TEAE leading to premature discontinuation

of treatment, any TEAE leading to premature discontinuation from the study, any TEAE leading to dose interruption of test article, and any serious TEAE leading to premature discontinuation of treatment dose.

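### In SAP Appendix 2 an imputed AE start date overrides a recorded stop month, so an event that ended before the first dose can be dated from it and counted as treatment-emergent when the start month is also unknown

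*SAP*

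**What the plan says.** Four rules in SAP 11.2 (Appendix 2) matter here.

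- A start date with day and month missing, under the condition "Y same as Y of first dose of study drug", becomes the first-dose date.
- A start date under the condition "None - date completely missing" also becomes the first-dose date.
- The first note settles conflicts in favour of a complete stop date: "if an estimated start date is after a complete stop date, use the first day of the stop date month".
- The second note settles conflicts with a partial stop date the other way: "if the estimated stop date is before a complete or imputed start date, use the last day of the start date month".

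SAP 9.1 then classifies by start date: "An AE is considered treatment emergent if the AE start date and time is on or after the start date and time" of the first administered dose. SAP 9.1 and the closing note of Appendix 2 add a default. If it cannot be settled whether the event came before or after the first dose, it counts as treatment-emergent.

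SAP 6.3 requires a query first. If the query fails, the substituted dates enter the calculations, while listings show what was recorded. Protocol 10.6.1 makes the split a reported result: "Adverse events are grouped into pre-treatment adverse events and treatment-emergent adverse events".

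**The concern.** The two notes treat the same information differently. A complete stop date before the first dose corrects a guessed start. A stop recorded as a month that ended before the first dose does not: the guessed start stands and the recorded month is replaced in the calculations. Yet the recorded month alone shows that the event was over before dosing.

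What is at stake is the division between pre-treatment and treatment-emergent events in a very small trial. SAP Section 3 reports 12 treated subjects, so one misplaced event is visible in a TEAE table. Pre-dose events can exist, because AEs are recorded from consent (Protocol 9.1.1) and subjects who are not well characterized may be screened about 2 months before baseline (Protocol 5.3).

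**Working it through.** The documents give no figure to reproduce, so the check applies the Appendix 2 rules to assumed dates.

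**Worked example.** Assumed: screening 25 April 2019, first dose 20 June 2019, last dose 10 January 2020, start date fully missing.

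| Step | Stop recorded as 31 May 2019 | Stop recorded as May 2019 |
|---|---|---|
| Start row | 20 June 2019 | 20 June 2019 |
| Stop row | 31 May 2019 (complete) | 31 May 2019 (last day of month) |
| Conflict | start after complete stop | estimated stop before imputed start |
| Note applied | first: start becomes 1 May | second: stop becomes 30 June |
| Result | 1 to 31 May 2019 | 20 to 30 June 2019 |
| SAP 9.1 start-date test | before first dose | on first dose: TEAE |

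Both records place the end of the event before 20 June. Only the missing stop day differs. A start recorded only as 2019 gives the same contrast.

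**Which patterns trigger it.** Assumed: screening 10 July 2019, first dose 12 September 2019, last dose 5 December 2019. From 10 July to 31 August there are 22 + 31 = 53 days, so the start/stop pairs with start on or before stop number 53 × 54 / 2 = 1,431. All end in a month before the first-dose month. The table gives the number dated on or after the first dose.

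| Start date recorded | Stop complete | Stop day missing |
|---|---|---|
| Complete | 0 of 1,431 | 0 of 1,431 |
| Day missing | 0 of 1,431 | 0 of 1,431 |
| Day and month missing, first-dose year | 0 of 1,431 | 1,431 of 1,431 |
| Fully missing | 0 of 1,431 | 1,431 of 1,431 |

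The stop month is overwritten in exactly the cells that show 1,431. The day-missing start is safe because the row "M and/or Y not same as date of first dose of study drug" keeps it in its recorded month. These counts show that the rule acts on every record of the pattern. They say nothing about how often the pattern occurs.

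**Across a year end.** Assumed: screening 10 December 2018, first dose 12 February 2019. A start recorded only as 2018 goes to the screening date and stays pre-dose. A fully missing start with a stop of December 2018 becomes 12 to 28 February 2019 and is again a TEAE.

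**Size.** With 12 treated subjects, one affected subject adds at most 1/12 = 8.3 percentage points to the incidence of a term. With the 14 allowed by the protocol synopsis it is 1/14 = 7.1. Both are maxima, because SAP 9.1 counts a subject once per preferred term.

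**The case against.** The best defence is the determinability sentence in SAP 9.1 and the closing note of Appendix 2. If a stop in May shows that the event ended before a June dose, the default is not triggered. Such an event also fails the opening definition in SAP 9.1, which asks for something new or worse on or after the start of treatment. On that view the SAP only leaves an order of precedence unstated.

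This shows that the result is not intended, but it does not prevent it. The default only adds events to the treatment-emergent class and takes none out. The start-date test stands beside it, and SAP 6.3 puts the substituted date into the calculations. Code that follows Appendix 2 as written gives the wrong class.

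The defence is right about reach. Well-characterized subjects under version 4.0 are screened on, or the day before, the first dosing day (Protocol 5.3 and 5.3.3). Versions 2.2 and 3.1, with 4 + 5 = 9 of the 12 treated subjects, put screening/baseline on Day 0. As far as the extracted tables can be read, they schedule AE collection from Day 1, although diagnostic screening could come earlier.

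A reader might also infer more than the documents support:

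- **That a missing stop day is enough.** It is not. The start month must be unknown too.
- **That misplaced events would look drug-related.** The investigator assigns relatedness (Protocol 9.4). It is not derived from imputed dates.
- **That other gaps in Appendix 2 add to the problem.** Year-only stop dates can give erratic durations, but SAP 9.1 plans no AE duration summary. No row covers a year-only start after the first-dose year, but such an event is post-dose on any imputed day, so its class does not change.

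**Conclusion.** The point holds in a narrow form. For a start date that is fully missing, or year-only in the first-dose year, combined with a stop recorded only as a month before the first-dose month, Appendix 2 yields an event that starts on the first-dose date and passes the SAP 9.1 test. The recorded month contradicts that, and so does the SAP's own limit on its default.

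It needs three things together: a pre-dose AE that ended in an earlier calendar month than the first dose, both dates incomplete in the way described, and a query that brought no answer. It affects calculations and tables, not listings. Few events, possibly none, should be affected, and each moves a TEAE rate by at most 8.3 points. The calendar dates above are assumptions; the conclusion rests only on the order of screening, stop month and first dose. This is a minor correction, worth making because a written rule gives a wrong answer and the repair is nearly free.

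**What to change.** Change Appendix 2 in three places.

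1. Extend the first note to partial stop dates. If the latest date that the recorded parts of the stop allow falls before the imputed start, move the start, not the stop. Use the first day of the recorded stop month, or the screening date if only the year is recorded and it is the screening year.
2. State that an imputed start date may not override a recorded stop month or year. Keep the second note for the remaining cases, such as a year-only stop that the table itself has set to the last-dose date.
3. State that an event whose recorded stop month or year lies wholly before the first dose is pre-treatment, and that the treatment-emergent default applies only to events this does not settle.

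The test in item 1 uses the recorded parts, not the substituted stop, for a reason. A stop recorded as 2020 may be set to a last dose on 10 January 2020. That should not pull back a start recorded as February 2020.

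The cost is a few lines of text and the matching lines in the date macro. No data collection changes.
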